2.3.3 Overall benefit-risk conclusion

Overall, the safety profile of somapacitan is similar to the well-known safety profile of daily growth hormone products e.g., Norditropin® and no new safety concerns have been found during the conduct of the somapacitan study program.

There are well known risks associated with administration of injectable medication³⁶ as well as procedural risks as described in [Table 2-1](#). In this study the risks associated with administration of trial product as well as the risks associated with the study procedures are expected to be comparable to what is seen in routine clinical practice.

More detailed information about the known and expected benefits and risks and reasonably expected adverse events (AE) of somapacitan may be found in the IB.

Taking into account the measures taken to minimise risk and burden to children participating in this study, the potential risks identified in association with somapacitan are justified by the anticipated benefits that may be afforded to children with SGA, TS, NS and ISS.

3 Objectives, endpoints and estimands

Table 3-1 Objectives and endpoints

Objectives	Endpoints		
Primary	Title	Time frame	Unit

 To evaluate the safety of once-weekly somapacitan in children, either naïve or non-naïve to GH treatment, within each of the four indications: SGA, TS, NS or ISS. 		Primary endpoint: Number of adverse events (AEs) From baseline (week 0) to week 26 Number of AEs	
		Secondary supportive safety endpoint: Number of adverse events (AEs) possibly or probably related to somapacitan From baseline (week 0) to week 26 Number of AEs	
Secondary	Title	Time frame	Unit

 To evaluate the long-term safety of once-weekly somapacitan in children, either naïve or non-naïve to GH treatment, within each of the four indications: SGA, TS, NS or ISS. 		Secondary supportive safety endpoint: Number of adverse events (AEs) From baseline (week 0) to week 156 Number of AEs	

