
 To evaluate the efficacy of once-weekly somapacitan in children, either naïve or non-naïve to GH treatment, within each of the four indications: SGA, TS, NS or ISS. 		Secondary supportive efficacy endpoints: Height Velocity From baseline (week 0) to week 26 cm/year Change in Height SDS From baseline (week 0) to week 26 Score * Change in Height Velocity SDS From baseline (week 0) to week 26 Score * Change in IGF-1 SDS From baseline (week 0) to week 26 Score * Change in IGFBP-3 SDS From baseline (week 0) to week 26 Score *	

 To evaluate the steady state pharmacokinetics of once-weekly somapacitan in children, either naïve or non-naïve to GH treatment, within each of the four indications: SGA, TS, NS or ISS. 		Secondary supportive efficacy endpoint: Weekly average somapacitan concentration (C_{avg}) based on population PK analysis From baseline (week 0) to week 26 ng/ml	

*Positive score indicates that the value is closer to or above the reference population compared to baseline

Primary estimand

The primary clinical question of interest is: What is the incidence of AEs from baseline to week 26 in the four populations (SGA, TS, NS or ISS) in all patients while on treatment regardless of dose reduction?

For the primary objective, the same primary estimand is defined for each of the four populations (SGA, TS, NS or ISS) with 5 attributes:

- The treatment condition of interest is defined as somapacitan regardless of dose reduction
- The population targeted by the clinical question: The treatment effect will be assessed separately for each of the four populations (SGA, TS, NS or ISS)
- Endpoint: Number of adverse events from baseline to 26 weeks
- Remaining intercurrent events:
 - Treatment discontinuation for any reason: Participants data will be included up to 14 days after treatment discontinuation. Data collected 14 days after the intercurrent event will be regarded as not relevant for estimation of the treatment effect
 - Dose reduction due to IGF-I or AE: Is addressed by the treatment condition of interest attribute

There are no remaining intercurrent events

- Population-level summary: Event rate per 100 patient years

Rationale for estimand: The primary estimand assesses the expected safety profile in relation to incidence of AEs for a future population (SGA, TS, NS or ISS) while on somapacitan treatment for 26 weeks, if no treatment discontinuation occurs for any reason.

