4.1 Overall design

This is an interventional, multi-national, multi-centre, open-labelled, uncontrolled phase 3 study with a basket design. The study is designed to evaluate safety and efficacy of once-weekly dosing of somapacitan 0.24 mg/kg/week during 26 weeks (main period) in children with short stature in each of the indications SGA, TS, NS and ISS. The 26-week main period will be followed by a 130-week extension period I with once-weekly dosing of somapacitan 0.24 mg/kg/week to evaluate long-term safety. Further, participants, who complete the extension period I when somapacitan is not available to be prescribed for children with SGA, TS, NS or ISS in their country, can continue treatment in extension period II which will last until somapacitan becomes available for prescription in their country or October 2027 (at the latest). Participants will receive somapacitan at 0.24 mg/kg/week. Study participants will include children with SGA, TS (only females), NS and ISS.

Children above or equal to 10.0 years (female participants with SGA, TS, NS, and ISS) or 11.0 years (male participants with SGA, NS, and ISS) and below 18.0 years are not included in the pivotal study NN8640-4467. Based on a recommendation from the Health Authorities, this age group will be investigated in this study NN8640-4469.

[figure not shown]
Approximately 60 participants in total are planned to be screened and up to 50 participants in total are planned to be enrolled (planned treated) in this study. In total, at least 40 participants are planned to complete the study. All participants will receive somapacitan 0.24 mg/kg/week.

The total treatment duration for participants in the study, up to the end of the extension period I, is scheduled to be 3 years. For participants who remain on treatment in the extension period II, the total study duration will be up to 5 years. The treatment period is followed by a safety follow-up period of 30 days.

The study consists of:

- an up to 3-week screening period for participants in the indications SGA and ISS
- an up to 6-week screening period for participants in the indications TS and NS
- a 26-week interventional main period
- a 130-week interventional extension period I
- up to 91-week interventional extension period II
- a 30-day follow-up period

Figure 4-1 Study design

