9.3.2 Primary endpoint/estimand analysis

The primary endpoint number of adverse events will be used to support the primary objective of evaluating safety of once-weekly somapacitan during 26 weeks of treatment in children with SGA, TS, NS or ISS based on the primary estimand corresponding to the on-treatment data points set.

To support the primary estimand descriptive statistics (Number and percentage of participants who experienced adverse events, the number of events) will be derived in addition to the event rate per 100 patient years of exposure. The primary endpoint will be summarised for each indication, SGA, TS, NS or ISS. All adverse events with onset after the first administration of trial product and up until end of treatment or 14 days after last trial product administration, whichever comes first, will be included in the analysis. The adverse events will be summarised by MedDRA (Medical Dictionary for Regulatory Activities) system organ class and MedDRA preferred term. Adverse events with onset 14 days or more after last trial product administration will be reported in a separate listing.

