9.3.3 Secondary endpoints/estimands analysis

Supportive Secondary Safety endpoints/estimands

The supportive secondary safety estimand regarding the incidence of AEs possibly or probably related to somapacitan from baseline up to week 26 of somapacitan treatment will be evaluated in a similar way as the primary endpoint including AEs possibly or probably related to somapacitan in the endpoint attribute.

The supportive secondary safety estimand regarding the incidence of AEs from baseline up to week 156 of somapacitan treatment will be evaluated in a similar way as the primary endpoint substituting 156 weeks for 26 weeks.

Supportive Secondary efficacy endpoints/estimands

Table 9-1 Overview of supportive secondary Efficacy endpoints

Title	Time frame	Unit	Details
Height velocity	From baseline (week 0) to visit 7 (week 26).	cm/year	Derived as HV at week 26 = (height at 26 weeks visit – height at baseline)/(time from baseline to 26 weeks visit in years).

Title	Time frame	Unit	Details
Change in Height SDS	From baseline (week 0) to visit 7 (week 26).	Score ^a	
Derived as the Height SDS value at baseline week 0 subtracted from the Height SDS value at week 26 (visit 7).
 
Height SDS is derived as:
 $\text{Height SDS}_i = \frac{\left(\frac{\text{Height}_i}{\text{population median}} \right)^{\text{Skewness}} - 1}{\text{Skewness} * \text{population SD}}$ 
where i indicates the visit. The population median and standard deviation are the ones corresponding to the age at visit i. The population median and standard deviation and skewness are based on reference data.²

Change in Height Velocity SDS	From baseline (week 0) to visit 7 (week 26).	Score ^a	
Derived as the Height Velocity SDS value at baseline week 0 subtracted from the Height Velocity SDS value at week 26 (visit 7). Height Velocity SDS is derived as:
 $\text{HV SDS}_i = \frac{\text{HV}_i - \text{population mean HV}}{\text{population SD}}$ 
where i indicates the visit. The population mean and standard deviation corresponding to the age at visit i. The population mean and standard deviation are based on reference data.^{2,53}

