#### 4.2.1 Definition of Endpoint

Number of adverse events (AEs) from baseline (week 0) to week 26.

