#### 4.3.2 Supportive Secondary Endpoints/Estimands

##### 4.3.2.1 Supportive secondary safety endpoints/estimands

The supportive secondary safety estimand regarding the incidence of AEs possibly or probably related to somapacitan from baseline up to week 26 of somapacitan treatment will be evaluated in a similar way as the primary endpoint including AEs possibly or probably related to somapacitan in the endpoint attribute.

The supportive secondary safety estimand regarding the incidence of AEs from baseline up to week

156 of somapacitan treatment will be evaluated in a similar way as the primary endpoint substituting 156 weeks for 26 weeks.

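### No adverse-event summary by exposure period is planned: the week 0–156 figure can be split only at week 26, so a rise confined to year 3 is diluted (a doubling shows as 1.33 times)

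*Protocol*

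**What the plan says.** Protocol Section 3 (Table 3-1) sets a secondary objective, "To evaluate the long-term safety of once-weekly somapacitan in children", and gives it one AE endpoint: the number of AEs from week 0 to week 156. Protocol 9.3.3 says that this "will be evaluated in a similar way as the primary endpoint substituting 156 weeks for 26 weeks", and SAP 4.3.2.1 uses the same rule ("substituting 156 weeks for 26 weeks").

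The method carried over is that of Protocol 9.3.2 and SAP 4.2. It gives "Number and percentage of participants who experienced adverse events, the number of events" and a rate, by system organ class and preferred term, separately for each indication. The estimand in Section 3 ends with "Population-level summary: Event rate per 100 patient years". The primary endpoint applies this method to the first window: "Number of adverse events (AEs) from baseline (week 0) to week 26" (SAP 4.2.1). The endpoint for AEs possibly or probably related to treatment also stops at week 26.

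Neither document plans an AE table by period or by year. SAP 4.5.2 limits AE displays to those of the primary and secondary endpoints. SAP 4.2.4 (supplementary analysis) and 4.5.1 (extent of exposure) are both marked as not applicable.

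Protocol 9.2 and SAP Section 3 close the On-treatment data points set at visit 7 (week 26) at the latest, and assign that set to the primary estimand and to all other safety data.

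**The concern.** Extension period I exists to evaluate long-term safety (Protocol 4.1). A reader of the long-term result will want to know whether AEs become more or less frequent, or change in kind, as exposure lengthens. One rate over three years answers that only if the rate is constant. If events rise late, the pooled rate averages them with two years of earlier exposure.

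Attrition adds to this. Participants enter at 10 or 11 to below 18 years, must stop treatment at near adult height or growth-plate closure (Protocol 7.1), and are not replaced (7.2.1). Year 3 will therefore hold less exposure than planned, from a selected group, and no planned AE output shows how many children are still at risk.

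For related AEs the gap is complete. With no summary beyond week 26, the later result cannot be obtained even by subtraction.

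**Working it through.** The plan states no AE rate, expected attrition or precision, so it has no figure to reproduce. Rates, sizes of rise and attrition below are assumptions; the window lengths and the 10 completers per indication (Protocol 9.5) come from the documents.

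**Exposure per indication, full retention.** The design has "a 26-week interventional main period" and "a 130-week interventional extension period I" (Protocol 4.1): 26 + 130 = 156 weeks, or 3 years. With 10 children:
- weeks 0–26: 10 × 26/52 = 5 patient-years (16.7% of 30)
- weeks 26–156: 10 × 130/52 = 25 patient-years (83.3%)
- weeks 104–156: 10 × 52/52 = 10 patient-years (33.3%)

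**Dilution.** If the rate is multiplied by k from some week onward, and a share w of exposure lies after that week, then cumulative rate / earlier rate = (1 − w) + w × k.

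| Rise starts at | w | k = 1.5 | k = 2 | k = 3 |
|---|---|---|---|---|
| week 26 | 130/156 | 1.42 | 1.83 | 2.67 |
| week 104 | 52/156 | 1.17 | 1.33 | 1.67 |
| week 130 | 26/156 | 1.08 | 1.17 | 1.33 |

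**What subtraction recovers.** Rate in weeks 26–156 = (events 0–156 − events 0–26) / (patient-years 0–156 − patient-years 0–26). Patient-years can be backed out of a reported count and rate, up to rounding. For a doubling confined to year 3 this gives (15 × 1 + 10 × 2)/25 = 1.40, little better than 1.33. It does not give the number of children with an event after week 26, because a child with events in both windows is counted in both.

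**Attrition (assumed).** With 10 children for two years and 6 in year 3, a year 3 doubling shows as (20 × 1 + 6 × 2)/26 = 1.23. With exponential attrition and a fraction r still on treatment at week 156, year 3 holds w = (r^(2/3) − r)/(1 − r) of exposure:
- r = 0.8: w = 0.309, doubling shows as 1.31
- r = 0.5: w = 0.260, 1.26
- r = 0.3: w = 0.212, 1.21

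Under the same three patterns, a doubling sustained from week 26 shows as 1.82, 1.78 and 1.74.

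**Example.** Take 200 AEs per 100 patient-years, doubling in year 3, full retention, exact Poisson 95% intervals:
- weeks 0–26: 10 events / 5 = 200 (96–368)
- weeks 0–156: 80 / 30 = 267 (211–332)
- weeks 26–156, by subtraction: 70 / 25 = 280 (218–354)
- weeks 104–156: 40 / 10 = 400 (286–545)
- weeks 0–104: 40 / 20 = 200 (143–272, the same 40 events over twice the exposure)

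The first three, which the plan can yield, do not separate. The last two do.

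**Limits of a split.** An exact conditional comparison of two Poisson rates (two-sided 5%, full retention) detects a year 3 doubling against years 1–2 with probability 52%, 83%, 95% and 99% at 100, 200, 300 and 400 AEs per 100 patient-years. For a 1.5-fold rise the range is 18% to 62%. Clustering of events within children would lower all of these.

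**Data points set.** If the visit 7 limit is applied as written, 130/156 = 83.3% of planned exposure falls outside the week 156 endpoint. The AE inclusion rule in Protocol 9.3.2 and SAP 4.2 runs instead to end of treatment or 14 days after the last dose, so the two definitions conflict.

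**The case against.** The strongest reply is that the long-term figure does not stand alone. The same summary, including system organ class and preferred term, is reported for weeks 0–26, and that window is only about one sixth of planned exposure. A reader might infer that early person-time swamps the cumulative rate, or that it hides any late rise. The documents do not support that. A rise that begins at week 26 and lasts keeps most of its size, and for all AEs the week 26–156 result follows by subtraction. This part of the reply stands, with one reservation: the week 0–26 rate rests on 5 patient-years and is itself imprecise.

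Second, the estimand asks for incidence to week 156, which a cumulative rate answers, and no text promises a time trend. That is right on the wording. It would go too far to say that the plan breaks a stated commitment; the point is that the chosen summary serves the long-term objective poorly.

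Third, there are other safeguards: an external data monitoring committee and an internal safety committee (Protocol 10.1.6), and laboratory, ECG and echocardiogram results by time of assessment (9.3.5). These help during the trial, but they do not put AEs by period into the planned analysis.

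Fourth, about 10 children per indication cannot support firm comparisons, and children still treated in year 3 differ from those who stopped. Both are true. They limit how the table may be read, but they are no reason to omit it from a study that is descriptive throughout (Protocol 9.1).

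**Conclusion.** The concern holds for changes within extension period I. No planned output shows how AEs develop between week 26 and week 156, and none shows related AEs after week 26. At full retention a doubling appears as 1.33 times if confined to year 3 and 1.17 times if confined to the last 26 weeks. Under the attrition patterns tried, the year 3 doubling appears as 1.21 to 1.31 times. It does not hold for a rise sustained from week 26, which would show as 1.83 times.

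The full-retention ratios rest only on the planned window lengths and an assumed step change in the rate. The attrition results, the example rates and the detection probabilities rest on figures that the documents do not give. This is a gap in description in a supportive study without hypothesis tests, not a threat to the primary endpoint.

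**What to change.** In Protocol 9.3.3 and SAP 4.3.2.1, keep the cumulative week 0–156 summary and add a descriptive table per indication for weeks 0–26, >26–52, >52–104 and >104–156. Each row should give children at risk, patient-years, events, rate per 100 patient-years and a 95% interval, for all AEs and for AEs possibly or probably related to treatment. Treatment is open-label, so the cut-points should be fixed now.

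In Protocol 9.2 and SAP Section 3, define an On-treatment data points set for this endpoint that runs to week 156 or 14 days after last administration, whichever comes first. Without it, every row after week 26 would be empty if the current definition is followed. Replace the not-applicable entry in SAP 4.5.1 with exposure by period.

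The cost is small: AE onset dates and dosing records are already collected, and the SAP rests on protocol version 3.0, so it needs updating for extension period II in any case. The downside is sparse cells, with 5, 5, 10 and 10 patient-years at full retention and fewer with attrition. A note under the table should say that the intervals are wide, that they ignore clustering of events within children if computed as Poisson, and that later rows describe a selected subset.

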10.7 Appendix 7: Tool for evaluation of inclusion criterium for height

Tool to assess Inclusion criteria – Impaired height

Below table ([Table 10-7](#)) must be used to assess the inclusion criteria for impaired height at screening. The table shows height measurements at both 2.5 and 2.0 SD below the mean for chronological age and sex in cm. Values in inches provided in [Table 10-7](#) have been calculated by Novo Nordisk in alignment with height tables prepared by Centers for Disease Control and Prevention.⁶⁷

Guideline to find the correct age in the table:

Age at screening must be provided in years, months, and days.

For example:

A child's date of birth is 10-Aug-2010

Screening date is 15-Sep-2022

Calculated age is 12 years, 1 month and 5 days at the screening visit.

Eligibility

Reference the specific SD in the inclusion criteria per indication in the study's protocol. To be eligible, the child's height must be equal to or below the height shown in the table below.

Table 10-7 Tool to assess Inclusion criteria – Impaired height

Age from				Age to			Boys				Girls			
Years	Month	Days		Years	Month	Days	SDS -2 (cm)	SDS -2 (inches)	SDS -2.5 (cm)	SDS -2.5 (inches)	SDS -2 (cm)	SDS -2 (inches)	SDS -2.5 (cm)	SDS -2.5 (inches)
9	11	22	-	10	0	6	125.0	49.2	121.9	48.0
10	0	7	-	10	0	21	125.2	49.3	122.1	48.1
10	0	22	-	10	1	6	125.4	49.4	122.3	48.1
10	1	7	-	10	1	21	125.6	49.4	122.4	48.2
10	1	22	-	10	2	6	125.7	49.5	122.6	48.3
10	2	7	-	10	2	21	125.9	49.6	122.7	48.3
10	2	22	-	10	3	6	126.1	49.6	122.9	48.4
10	3	7	-	10	3	21	126.3	49.7	123.1	48.4
10	3	22	-	10	4	6	126.4	49.8	123.2	48.5
10	4	7	-	10	4	21	126.6	49.8	123.4	48.6
10	4	22	-	10	5	6	126.8	49.9	123.5	48.6
10	5	7	-	10	5	21	127.0	50.0	123.7	48.7
10	5	22	-	10	6	6	127.2	50.1	123.9	48.8
10	6	7	-	10	6	21	127.4	50.1	124.1	48.8
10	6	22	-	10	7	6	127.6	50.2	124.2	48.9
10	7	7	-	10	7	21	127.7	50.3	124.4	49.0
10	7	22	-	10	8	6	127.9	50.4	124.6	49.0
10	8	7	-	10	8	21	128.1	50.5	124.8	49.1
10	8	22	-	10	9	6	128.3	50.5	125.0	49.2
10	9	7	-	10	9	21	128.6	50.6	125.1	49.3
10	9	22	-	10	10	6	128.8	50.7	125.3	49.3
10	10	7	-	10	10	21	129.0	50.8	125.5	49.4

Age from			Age to			Boys				Girls				
Years	Month	Days	Years	Month	Days	SDS -2 (cm)	SDS -2 (inches)	SDS -2.5 (cm)	SDS -2.5 (inches)	SDS -2 (cm)	SDS -2 (inches)	SDS -2.5 (cm)	SDS -2.5 (inches)	
10	10	22	-	10	11	6	.	.	.	129.2	50.9	125.7	49.5	
10	11	7	-	10	11	21	.	.	.	129.4	51.0	125.9	49.6	
10	11	22	-	11	0	6	129.8	51.1	126.5	49.8	129.6	51.0	126.1	49.7

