11	0	7	-	11	0	21	130.0	51.2	126.7	49.9	129.9	51.1	126.3	49.7
11	0	22	-	11	1	6	130.2	51.3	126.9	49.9	130.1	51.2	126.6	49.8
11	1	7	-	11	1	21	130.4	51.3	127.0	50.0	130.3	51.3	126.8	49.9
11	1	22	-	11	2	6	130.6	51.4	127.2	50.1	130.6	51.4	127.0	50.0
11	2	7	-	11	2	21	130.7	51.5	127.4	50.2	130.8	51.5	127.2	50.1
11	2	22	-	11	3	6	130.9	51.5	127.6	50.2	131.1	51.6	127.5	50.2
11	3	7	-	11	3	21	131.1	51.6	127.8	50.3	131.3	51.7	127.7	50.3
11	3	22	-	11	4	6	131.3	51.7	127.9	50.4	131.6	51.8	127.9	50.4
11	4	7	-	11	4	21	131.5	51.8	128.1	50.4	131.9	51.9	128.2	50.5
11	4	22	-	11	5	6	131.7	51.8	128.3	50.5	132.1	52.0	128.4	50.6
11	5	7	-	11	5	21	131.9	51.9	128.5	50.6	132.4	52.1	128.7	50.7
11	5	22	-	11	6	6	132.1	52.0	128.7	50.7	132.7	52.2	128.9	50.8
11	6	7	-	11	6	21	132.3	52.1	128.9	50.7	132.9	52.3	129.2	50.9
11	6	22	-	11	7	6	132.5	52.2	129.1	50.8	133.2	52.5	129.5	51.0
11	7	7	-	11	7	21	132.7	52.2	129.3	50.9	133.5	52.6	129.8	51.1
11	7	22	-	11	8	6	132.9	52.3	129.5	51.0	133.8	52.7	130.0	51.2
11	8	7	-	11	8	21	133.1	52.4	129.7	51.1	134.1	52.8	130.3	51.3
11	8	22	-	11	9	6	133.3	52.5	129.9	51.1	134.4	52.9	130.6	51.4
11	9	7	-	11	9	21	133.5	52.6	130.1	51.2	134.7	53.0	130.9	51.5
11	9	22	-	11	10	6	133.7	52.6	130.3	51.3	135.0	53.1	131.2	51.7

Age from			Age to			Boys				Girls				
Years	Month	Days	Years	Month	Days	SDS -2 (cm)	SDS -2 (inches)	SDS -2.5 (cm)	SDS -2.5 (inches)	SDS -2 (cm)	SDS -2 (inches)	SDS -2.5 (cm)	SDS -2.5 (inches)	
11	10	7	-	11	10	21	133.9	52.7	130.5	51.4	135.3	53.3	131.5	51.8
11	10	22	-	11	11	6	134.2	52.8	130.7	51.5	135.6	53.4	131.8	51.9
11	11	7	-	11	11	21	134.4	52.9	130.9	51.5	135.9	53.5	132.1	52.0
11	11	22	-	12	0	6	134.6	53.0	131.1	51.6	136.2	53.6	132.4	52.1
12	0	7	-	12	0	21	134.8	53.1	131.3	51.7	136.5	53.8	132.7	52.3
12	0	22	-	12	1	6	135.0	53.2	131.6	51.8	136.8	53.9	133.0	52.4
12	1	7	-	12	1	21	135.3	53.3	131.8	51.9	137.2	54.0	133.3	52.5
12	1	22	-	12	2	6	135.5	53.3	132.0	52.0	137.5	54.1	133.7	52.6
12	2	7	-	12	2	21	135.7	53.4	132.2	52.1	137.8	54.2	134.0	52.7
12	2	22	-	12	3	6	136.0	53.5	132.4	52.1	138.1	54.4	134.3	52.9
12	3	7	-	12	3	21	136.2	53.6	132.7	52.2	138.4	54.5	134.6	53.0
12	3	22	-	12	4	6	136.4	53.7	132.9	52.3	138.7	54.6	134.9	53.1
12	4	7	-	12	4	21	136.7	53.8	133.1	52.4	139.0	54.7	135.2	53.2
12	4	22	-	12	5	6	136.9	53.9	133.3	52.5	139.3	54.8	135.6	53.4
12	5	7	-	12	5	21	137.2	54.0	133.6	52.6	139.6	55.0	135.9	53.5
12	5	22	-	12	6	6	137.4	54.1	133.8	52.7	139.9	55.1	136.2	53.6
12	6	7	-	12	6	21	137.7	54.2	134.0	52.8	140.2	55.2	136.5	53.7

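### The skewness-type SDS formulas for height, IGF-I, IGFBP-3 and sitting height/height divide by a population SD where a coefficient of variation is needed, so followed literally they return the true SDS divided by the median

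*Protocol*

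**What the plan says.** Protocol Section 9.3.3 (Table 9-1) gives one formula shape for height, IGF-I and IGFBP-3 SDS. The measured value is divided by the population median, raised to the power Skewness, reduced by 1, and divided by the product of Skewness and population SD. Section 9.3.6 (Table 9-2) uses the same shape for the sitting height/height SDS. SAP Section 6.1 (Appendix 1) repeats all four, and SAP Section 4.8 declares no changes to the planned analysis.

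The text under the formulas calls the spread term a standard deviation: "The population median and standard deviation are the ones corresponding to the age at visit i". For height, IGF-I and IGFBP-3 it continues: "The population median and standard deviation and skewness are based on reference data". The sitting height/height row cites no reference source. Neither document mentions a coefficient of variation or an S parameter.

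The height velocity SDS row of Table 9-1 uses the same label in a linear formula, (HV − mean)/SD, with the note "The population mean and standard deviation corresponding to the age at visit i" and then "The population mean and standard deviation are based on reference data". The parental height SDS in Table 9-2 is linear in the same way.

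Protocol Section 10.7 (Table 10-7) gives an internal yardstick for height: "The table shows height measurements at both 2.5 and 2.0 SD below the mean for chronological age and sex in cm".

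**The concern.** A value divided by its median has no unit, and neither does a power of it. To turn that number into SD units, the divisor must also be free of units, which means SD/median. An SD in cm or ng/mL leaves a result whose size depends on the unit of measurement, and a standard deviation score must not do that.

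The label cannot safely be taken as shorthand, because in the height velocity and parental height formulas the same words must mean an ordinary SD in measurement units.

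The formula defines three named supportive secondary endpoints (change in height, IGF-I and IGFBP-3 SDS), their week 52 counterparts, the sitting height/height SDS, and the change in height SDS at near adult height. The index of genetic height potential subtracts a linear parental SDS from the SDS at near adult height. If that second score uses the height formula as written, the two terms are on different scales.

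**Working it through.** **Inputs.** Heights at −2 and −2.5 SDS come from protocol Table 10-7. The girls' entries for the row covering age 10 years 0 months read "125.0 49.2 121.9 48.0" and the boys' entries for 12 years 0 months read "134.6 53.0 131.1 51.6" (cm, inches at −2; cm, inches at −2.5). Boys at 14 years 0 months are 147.2 and 142.9 cm. The documents give no medians, SDs or Skewness values, so these are solved from the table or assumed.

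**Algebra.** Write M for the median, L for Skewness and S = SD/M. The power-transform score is z = ((X/M)^L − 1)/(L × S). The plan divides by L × SD = L × M × S, so the written result is z/M for any L. With L = 1 it reduces to (X − M)/(M × SD), the ordinary SDS divided by the median.

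**Height with L = 1.** Here SD = (height at −2 minus height at −2.5)/0.5 and M = height at −2 plus 2 × SD.

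- Girl, 10.0 years: SD = (125.0 − 121.9)/0.5 = 6.2 cm; M = 125.0 + 12.4 = 137.4 cm. As written: (125.0/137.4 − 1)/6.2 = −0.0146. Table 10-7 says −2.
- Boy, 12.0 years: SD = 7.0 cm; M = 148.6 cm. As written: (134.6/148.6 − 1)/7.0 = −0.0135.
- Boy, 14.0 years: SD = 8.6 cm; M = 164.4 cm. As written: (147.2/164.4 − 1)/8.6 = −0.0122.
- The same 12-year-old boy in inches: SD = (53.0 − 51.6)/0.5 = 2.8; M = 58.6. As written: (53.0/58.6 − 1)/2.8 = −0.034. One child has two scores, depending on the unit.

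**Other Skewness values.** Solving M and S again with L = −1.5, about 0, 1 and 2.5 gives −0.0132 to −0.0136 for the 12-year-old boy. Over the rows checked between 10 and 18 years, the −2 SDS heights return about −0.011 to −0.015. A true gain of 0.30 SDS at a fixed median of 148.6 cm returns 0.30/148.6 = 0.002.

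With SD/median as divisor, the table heights return −2.00 and −2.50. That is true by construction, because M and S were solved from those heights. The factor 1/M does not depend on that step.

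**Other measures, true SDS −2, assumed medians.**

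| Measure | Assumed median | As written |
|---|---|---|
| IGF-I, ng/mL | 150 to 500 | −0.013 to −0.004 |
| IGFBP-3, ng/mL | 3000 to 7000 | −0.0007 to −0.0003 |
| IGFBP-3, mg/L | 3 to 7 | −0.67 to −0.29 |
| Sitting height/height, ratio | 0.50 to 0.55 | −4.0 to −3.6 |
| Sitting height/height, percent | 50 to 55 | about −0.04 |

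Each entry is −2 divided by the median. Table 9-2 treats sitting height/height as a ratio, so its median is below 1 and the score is inflated about 1.8 to 2 times.

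**The case against.** The best defence is that this is a fault of labelling. The four formulas take a matched set of median, skewness and spread from reference data. If that source is an L/M/S table and the programmer uses its S, the results are correct. The height velocity row is a different, linear method built on a mean, so its use of the label does not by itself settle what the term means elsewhere. This defence is plausible, but neither document states it, and for sitting height/height no source is named that could resolve the term.

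It is also fair to say that a height score of about −0.01 for every child would probably be noticed, since treatment-naïve children must be at least 2.0 or 2.5 SD below the mean at entry. That argues for modest importance; it does not make the formula right.

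Three stronger readings are tempting and are not supported:

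- That all four scores collapse towards 0. This is shown from the documents for height only. It holds for IGF-I under an assumed median, depends on the unit for IGFBP-3, and is the reverse for the sitting-height ratio.
- That the trial's SDS results will be wrong. The documents show a faulty specification, not how it was or will be programmed.
- That eligibility or IGF-I monitoring is affected. Height eligibility is read from Table 10-7 in cm or inches. Nothing says the Table 9-1 formula produces the IGF-I SDS values used during the trial under Section 6.5.1.

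**Conclusion.** The specification is wrong as written in both documents. Taken literally, the four formulas return the true SDS divided by the median, whatever the Skewness. For height the size of the error follows from the protocol's own table: about −0.011 to −0.015 where −2 is intended. For the other three measures the size, and for sitting height/height the direction, rests on assumed medians and units.

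The stakes are limited. The affected measures are supportive secondary endpoints or other parameters, summarised descriptively, and no hypothesis is tested. The primary adverse event endpoint, height velocity in cm/year and height velocity SDS do not use these formulas. The point deserves correction because a reader who follows the stated endpoint definition cannot reproduce the protocol's own height table.

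**What to change.** In the height, IGF-I and IGFBP-3 rows of protocol Table 9-1, the sitting height/height row of Table 9-2, and the four matching rows of SAP Appendix 1, replace population SD with population coefficient of variation (S = SD/median). Make the same replacement in the sentences beneath these formulas, which now say standard deviation; otherwise formula and text will disagree. Keep population SD only in the height velocity SDS and parental height SDS formulas. Name the reference source for sitting height/height in the same edit.

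The cost is wording only, with no new data and no change of design. Results already programmed with S would not change. Running the Table 10-7 heights through the analysis program and confirming −2.0 and −2.5 would show which quantity has been used for height.
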